3.9 Subject site transfers

Subjects may have transferred from one site to another through the course of participation in the study. Subjects that transferred from one site to another site, for whatever reason, have generally retained their subject number. However, in some cases, the subject number changed. When this is true, the most recently assigned subject number will be used for analyses and subject data listings. A record of any change in subject numbers will be presented in the Section 13.2.

4 STATISTICAL/ANALYTICAL ISSUES

4.1 Adjustments for covariates

No statistical testing is planned; therefore, this section is not applicable.

4.2 Handling of dropouts or missing data

Seizure frequency (subjects with POS) and seizure days (subjects with PGS) will be calculated over non missing diary days during each study period or time interval as described in Section 3.2.4 and Section 3.2.5; diary days for which seizure data were not obtained will not be considered in the calculation of seizure frequency or seizure days. Because the evaluation of efficacy is not the primary objective of this study, and because this is an uncontrolled study in a variable setting, which allows individualized optimization of dosing

of BRV and concomitant AEDs, no summaries assessing the impact of missing seizure diary days are planned.

For subjects who prematurely discontinue during the Evaluation Period, the calculation of POS frequency and PGS seizure days will be based on available seizure diary while the subject was receiving BRV. The presence of such dropouts may influence the evaluation of the long-term outcomes for subjects who either do not discontinue or do not discontinue early in the study. Therefore, as described below, selected summaries will be produced by exposure duration cohorts to allow an assessment of long-term outcomes without the potentially confounding influence of earlier discontinuations.

4.3 Interim analyses and data monitoring

Interim summaries were produced to support regulatory submissions for marketing authorization while this study is ongoing. There are no statistical concerns with such interim assessments for this study design.

4.4 Multicenter studies

Efficacy and safety outcomes will not be assessed for individual investigator sites due to the low expected number for enrollment within each investigator site.

4.5 Multiple comparisons/multiplicity

No statistical testing is planned; therefore, this section is not applicable.

4.6 Use of an “Efficacy Subset” of subjects

All subjects who receive at least 1 dose of study drug and have at least 1 diary record during the Evaluation Period will be included in efficacy summaries. No additional efficacy subsets are defined for this study.

4.7 Active-control studies intended to show equivalence

This section is not applicable for this study.

4.8 Examination of subgroups

Selected summaries will be provided for the following subgroups as specified within each of the following sections:

- Two mappings of countries to regions are defined, 1 based on the classification requested by Food and Drug Administration (FDA), and 1 based on the regional classification for the CHMP (Committee for Medicinal Products for Human Use).

Countries will be mapped to geographic regions as follows for the FDA:

Geographic Region (FDA)	Country
North America	Canada, United States, Puerto Rico
Latin America	Brazil, Mexico
Western Europe	Austria, Belgium, Finland, France, Germany, Ireland, Italy, Netherlands, Norway, Réunion, Spain, Sweden, United Kingdom, Switzerland
Eastern Europe	Bulgaria, Czech Republic, Estonia, Latvia, Hungary, Lithuania, Poland, Romania, Russia, Serbia and Montenegro, Turkey, Ukraine
Asia/Pacific/Other	Australia, Hong Kong, India, Israel, Japan, Singapore, South Africa, Republic of Korea, Taiwan, Tunisia

Countries will be mapped to geographic regions as follows for the CHMP:

Geographic Region (CHMP)	Country
North America	Canada, United States, Puerto Rico
Latin America	Brazil, Mexico
Europe (European Union [EU] member states) *	Austria, Belgium, Bulgaria, Czech Republic, Estonia, Finland, France, Germany, Hungary, Ireland, Italy, Latvia, Lithuania, Netherlands, Norway, Poland, Réunion, Romania, Spain, Sweden, United Kingdom
Europe (non-EU member states)	Russia, Serbia and Montenegro, Switzerland, Turkey, Ukraine
Asia/Pacific/Other	Australia, Hong Kong, India, Israel, Japan, Singapore, South Africa, Republic of Korea, Taiwan, Tunisia

* EU member states plus Norway.

- Seizure type (Partial Onset Seizures, Primary Generalized Seizures)
- Randomized treatment in the previous study (placebo [PBO], BRV) (TEAEs only)

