3.2 Secondary objective

- To evaluate the maintenance of efficacy of BRV over time

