5.4 Rationale for study design and selection of dose

In the previous study N01358, subjects will be randomized to an oral dose of BRV 100mg/day, BRV 200mg/day, or to matching PBO. In the previous study N01258, subjects will receive either a 60-second iv bolus or a 15-minute iv infusion at a dose of BRV 100mg twice daily (200mg/day). Previous Phase 2/3 clinical studies in POS and dose-response modeling suggest that optimal seizure frequency requires BRV doses of 50 to 100mg/day, with BRV 150mg/day possibly providing some additional benefit. Following consultation with regulatory authorities, it was recommended to also explore BRV 200mg/day to obtain data on the upper end of the dose response curve in N01358.

The starting doses in N01379 will be BRV 150mg/day for subjects from N01358 and BRV 200mg/day for subjects from N01258. The study entry doses will be taken as 2 equally divided oral doses administered twice daily. In Phase 2/3 studies for POS with BRV doses up to 150mg/day, the overall discontinuation rate and the discontinuation rate due to TEAEs was low and similar to PBO. The most frequently reported TEAEs at BRV doses up to 150mg/day were headache, somnolence, dizziness, and fatigue. The BRV dose can be adjusted based on the individual subject's seizure control and/or tolerability after the first 2 weeks, up to a maximum dose of BRV 200mg/day.

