7.2 Treatments to be administered

Subjects from N01358 will be started on a BRV dose of 150mg/day (2 equally divided doses administered twice daily) at study entry and should be maintained at this dose for at least 2 weeks, unless the subject is not able to tolerate treatment. Subjects from N01258 will be started at a BRV dose of 200mg/day (2 equally divided doses administered twice daily) and should be maintained at this dose for at least 2 weeks, unless the subject is not able to tolerate treatment. The BRV dose can subsequently be adjusted based on the individual subject's seizure control and/or tolerability. However, the BRV dose should not exceed 200mg/day during the study.

The first intake of study medication should occur in the evening of the day of the Entry Visit (EV). Subjects should take tablets according to instructions provided by the Investigator.

During the Down-Titration Period, the BRV dose may be decreased in steps of a maximum of 50mg/day on a weekly basis. A last down-titration step at 20mg/day for 1 week should be included prior to the Posttreatment Period.

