3.2 Analysis time points

3.2.1 First and last dose of BRV

Unless otherwise noted, all references to the first dose of BRV in this SAP refer to the first dose of BRV during N01379 (ie, not the first dose of BRV from the previous study in which subjects participated in prior to N01379). Unless otherwise noted, all references to the last known dose of BRV in this SAP refer to the last dose of BRV taken across any study periods (ie, not necessarily the last dose of BRV during the Evaluation Period).

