8.1.1 Partial onset seizure frequency

Twenty-eight day adjusted POS frequency will be summarized with quantitative descriptive statistics for all subjects for the Baseline Period, the On Treatment Period, and by 3-month time intervals over the On Treatment Period. The summary over the On Treatment Period will include all subjects in the POS Efficacy Analysis Set. Similar summaries will be provided for the full cohort interval and by 3-month time intervals for each exposure duration cohort.

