11.2.2 General summaries of TEAEs

Pre-treatment AEs will be provided in a subject data listing; no summaries of pre treatment AEs are planned.

An overall summary of AEs will provide the overall number of TEAEs and the numbers and percentages of subjects with at least 1 TEAE, with a TEAE that led to permanent discontinuation of study drug, with a drug-related TEAE, with a severe TEAE, with a treatment-emergent SAE, and with a drug-related treatment-emergent SAE. The number and percentage of subjects who died will also be summarized. This summary will be provided for all subjects in the Safety Analysis Set and also by subgroup for geographic region and seizure type.

The following summaries of TEAEs will be provided by MedDRA SOC and PT. All summaries are for the combined Evaluation, Down-Titration, and Post-Treatment Periods unless otherwise indicated.

Overall Incidence Summaries

- Incidence of TEAEs
- Incidence of TEAEs by 3-month time interval
- Incidence of TEAEs by study period (Evaluation, Down-Titration, Post-Treatment)
- Incidence of TEAEs for TEAEs occurring in at least 5% of subjects
- Incidence of TEAEs by 3-month time intervals for TEAEs occurring in at least 5% of subjects overall
- Incidence of non-serious TEAEs occurring in at least 5% of subjects

The incidence of TEAEs occurring in at least 5% of subjects will be summarized overall as noted above and also by subgroup for geographic region, seizure type, and randomized treatment from the previous double-blind study.

A subject is included in a 3-month interval if the subject was receiving BRV at any time during that interval based on their duration of exposure to BRV (eg, a subject with exposure for 91 days is included in the time interval for Months 1-3 and Months 4-6). Summaries of AEs by 3-month intervals will include all subjects who are classified into each time interval as defined above. TEAEs which had onset prior to or on the date of the last dose of BRV) are included in summaries by 3-month time intervals.

Maximum Intensity and Causality

- Incidence of TEAEs by maximum intensity
- Incidence of drug-related TEAEs

Serious Adverse Events

- Incidence of treatment-emergent SAEs

Discontinuations due to TEAE

- Incidence of TEAEs leading to permanent discontinuation of study drug

TEAEs of interest

AEs of interest will be identified based on MedDRA search criteria, which are documented outside of the SAP. The following summaries will be provided for AEs of interest:

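### Efficacy tables pool ex-placebo subjects with subjects already on BRV, so onset and maintenance of effect are mixed; the prior-treatment split should be extended from TEAEs to the three POS outcomes

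*SAP*

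**What the plan says.** The objective is "To evaluate the maintenance of efficacy of BRV over time" (Protocol 3.2; SAP 2.1.2 agrees). In N01358, "subjects will be randomized to an oral dose of BRV 100mg/day, BRV 200mg/day, or to matching PBO" (Protocol 5.4). Protocol 7.2 then gives one entry dose whatever the prior arm: "Subjects from N01358 will be started on a BRV dose of 150mg/day (2 equally divided doses administered twice daily) at study entry". So at entry one group meets BRV for the first time and the other two change dose.

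SAP 3.6 presents all subjects as one arm by default. For POS frequency, "The summary over the On Treatment Period will include all subjects in the POS Efficacy Analysis Set" (SAP 8.1.1), with further tables by 3-month interval and by exposure duration cohort. SAP 8.1.2 and 8.1.3 treat percent reduction and responders in the same way, and geographic region is the only subgroup they add. Change is measured from the Baseline of the previous study.

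Time zero is the first N01379 dose, "not the first dose of BRV from the previous study in which subjects participated in prior to N01379" (SAP 3.2.1), and SAP 3.2.5 counts the 3-month intervals from that day.

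Prior arm appears in SAP 4.8 as "Randomized treatment in the previous study (placebo [PBO], BRV) (TEAEs only". It is used in SAP 11.2.2, where TEAEs occurring in at least 5% of subjects are shown "also by subgroup for geographic region, seizure type, and randomized treatment from the previous double-blind study". No section on efficacy uses it.

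**The concern.** To maintain an effect is to keep one already obtained. For an ex-BRV subject, Months 1-3 follow a completed BRV treatment period. For an ex-placebo subject, the same interval is first exposure. One column averages the two, so a rise, a level line or a fall in the pooled table has no single meaning.

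The exposure duration cohorts do not help. SAP 4.2 introduces them to deal with earlier discontinuation, and they count N01379 exposure only. A cohort with at least 12 months of exposure therefore still mixes subjects with different total time on BRV.

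All efficacy summaries are descriptive, so a reader judges maintenance from the shape of these tables alone. The SAP treats prior arm as relevant for TEAEs but leaves it out of the outcomes that address the maintenance objective.

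**Working it through.** **Inputs from the documents.** There are three prior arms and one entry dose. Efficacy is pooled, and there is no test, margin or power figure to reproduce. The only relevant number is 650 to 720 expected entrants from N01358 (Protocol 12.9). It rests on at least 90% of those randomized, but the number randomized is not given, so it cannot be re-derived.

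**Assumed.** The ex-placebo share *w* is taken as 1/3 (equal arms), with a range of 1/4 to 1/2. At 1/3, 650/3 to 720/3 gives about 217 to 240 subjects per prior arm.

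**Step 1: dilution.** Let *L* be the loss in ex-BRV subjects between two intervals and *G* the gain in ex-placebo subjects. For a mean or a proportion,

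pooled change = *w*·*G* − (1 − *w*)·*L*.

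This does not hold exactly for medians. With *L* = 10 points and *G* = 0:

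| *w* | Pooled change |
|---|---|
| 1/4 | −0.75 × 10 = −7.5 |
| 1/3 | −0.667 × 10 = −6.7 |
| 1/2 | −0.50 × 10 = −5.0 |

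**Step 2: offset.** The pooled change is zero when *L* = *G*·*w*/(1 − *w*). Each point of ex-placebo gain hides 1/3, 1/2 or 1 point of ex-BRV loss at *w* = 1/4, 1/3 or 1/2. At *w* = 1/3, hiding a 10-point loss completely needs a 20-point gain.

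**Step 3: how large the gain could be.** Only a gain that comes after Months 1-3 can offset a later loss. Suppose the ex-placebo mean percent reduction steps from 15% to 40% (assumed values) after *d* days of Days 1-90. The later gain is then *G* = 25·*d*/90.

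| Delay *d* (days) | Later gain *G* | Loss hidden at *w* = 1/3 |
|---|---|---|
| 0 | 0 | 0 |
| 7 | 1.9 | 1.0 |
| 14 | 3.9 | 1.9 |
| 30 | 8.3 | 4.2 |
| 45 | 12.5 | 6.2 |

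At 30 days the hidden loss is 2.8 points for *w* = 1/4 and 8.3 points for *w* = 1/2.

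**Step 4: interval by interval.** Take assumed responder rates at *w* = 1/3. Ex-BRV subjects decline steadily, and ex-placebo onset is complete by the second interval.

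| Interval | Ex-placebo | Ex-BRV | Pooled |
|---|---|---|---|
| Months 1-3 | 30 | 45 | (30 + 2×45)/3 = 40 |
| Months 4-6 | 45 | 42.5 | (45 + 2×42.5)/3 = 43.3 |
| Months 7-9 | 45 | 40 | (45 + 2×40)/3 = 41.7 |
| Months 10-12 | 45 | 37.5 | (45 + 2×37.5)/3 = 40 |

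The first and last pooled values agree although ex-BRV subjects lost 7.5 points. The intermediate values do show a decline: 3.3 points from Months 4-6 to Months 10-12, against 5 in ex-BRV subjects.

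**The case against.** The strongest reply is that the pooled tables do what the protocol asks. Protocol 4.2.1 sets the previous study's Baseline as the reference for percent reduction and response, and Protocol 12.2 calls for summaries of all subjects combined. Efficacy is secondary and descriptive, and no test, sample size or safety result changes. All of this stands, and it makes the split an addition to the pooled tables.

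A second reply is that the difficulty fades. N01358 subjects start at 150 mg/day without up-titration, so the documents give no reason to expect slow onset. Once established on BRV, ex-placebo subjects can themselves show maintenance or loss, and follow-up runs for years (SAP 5.1 estimates retention to 60 months). This largely stands for the offset. It does not remove the dilution: a decline confined to ex-BRV subjects stays understated in every interval.

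A reader might infer from equal pooled values at Months 1-3 and Months 10-12 that the curve would look flat and hide the loss. The documents do not support that. The SAP tabulates every interval, and Step 4 shows the decline in between. A flat line throughout needs ex-placebo gains that keep cancelling the loss for most of a year.

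A reader might also infer that maintenance should rest on ex-BRV subjects alone, judged against their N01358 treatment result. That goes too far. It sets aside valid later data from ex-placebo subjects and departs from the protocol's reference. It would also compare blinded fixed-dose treatment with open-label treatment in which BRV dose and concomitant AEDs may change (SAP 2.3). The SAP brings in N01358 Baseline diary data, but no section brings in diary data from the N01358 Treatment Period.

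**Conclusion.** The point holds in limited form. Efficacy is pooled over prior arms, the prior-treatment split is confined to TEAEs, and nothing else in the SAP separates first exposure from continued exposure. The 3-month POS tables therefore mix onset with maintenance.

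Dilution is the firm part: an ex-BRV loss appears at 1 − *w* of its size when ex-placebo subjects do not change. The further offset is partial and mainly early. It becomes complete only with slow ex-placebo onset or a large ex-placebo share. The share, onset delay and response levels used here are all assumptions, since the documents state none of them.

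This is a worthwhile, inexpensive improvement to a secondary descriptive analysis. It is not a defect in the primary safety evaluation.

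**What to change.** In SAP 4.8, replace the restriction to TEAEs with: *TEAEs and, for N01358 subjects, the 8.1.1 to 8.1.3 outcomes*. For those outcomes use three levels: prior placebo, BRV 100 mg/day and BRV 200 mg/day. Add the POS frequency, percent-reduction and responder tables by 3-month interval for each level. Keep the pooled tables, and read maintenance from both together. SAP 8 already excludes N01258 subjects from percent reduction and responders; in the POS frequency table they would stay in the pooled column only.

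Optionally, show an N01358 Treatment Period value for the two ex-BRV levels if those diary data are available. The split alone would not reveal a loss between N01358 treatment and Months 1-3. Such a column should carry the caveat that it compares blinded fixed-dose with open-label flexible-dose treatment.

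The cost is a change of SAP wording and repeat runs of three planned tables, using a subgroup variable already planned for TEAEs. No visit, dose or data collection changes. The downside is more table pages and smaller groups per column, which shrink further in later intervals as subjects leave.

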5 STUDY POPULATION CHARACTERISTICS

5.1 Subject disposition

Due to differences in data format across studies, in order to facilitate summary of subject disposition, the reasons for discontinuation for individual studies will be collapsed as follows for summaries:

LTFU Category	CRF Reason
ADVERSE EVENT	ADVERSE EVENT
LACK OF EFFICACY	LACK OF EFFICACY
	LOSS OF EFFICACY
LOST TO FOLLOW-UP	LOST TO FOLLOW-UP
SUBJECT CHOICE	CONSENT WITHDRAWN
	WITHDRAWAL OF CONSENT FOR PERSONAL REASONS NOT RELATED TO AES
	WITHDRAWAL OF CONSENT FOR PERSONAL REASONS NOT RELATED TO AES OR LACK OF EFFICACY
OTHER	PROTOCOL VIOLATION
	OTHER REASON
	OTHER
MISSING	If subject discontinued the study and the termination CRF is not available

Only 1 primary reason for discontinuation should have been reported. In the event that more than 1 reason is specified in the clinical database, both reasons will be summarized and a footnote will be added to the summary table to indicate that at least 1 subject is counted for multiple reasons for discontinuation.

An overall summary of disposition will be provided for all enrolled subjects (ie, all subjects who signed informed consent). The following will be summarized:

- The number of subjects in the Safety Analysis Set
- The number of subjects excluded from the Safety Analysis Set
- The number of subjects completed the study
- The number of subjects discontinued from the study, including the reason for discontinuation. If subject discontinued the study and the termination CRF is not available, the reason for discontinuation will be reported as “MISSING”.

Additionally, an overall summary of disposition will present the following for subjects in the Safety Analysis Set:

- The number of subjects completed the study
- The overall number of subjects discontinued and the number of subjects discontinued by primary reason for discontinuation. If subject discontinued the study and the termination CRF is not available, the reason for discontinuation will be reported as “MISSING”.

Overall subject disposition will also be summarized by geographic region and seizure type for the Safety Analysis Set.

The number of subjects within each geographic region and the number of subjects within each seizure type will be summarized for the Safety Analysis Set.

Kaplan-Meier estimates of the percentage of subjects completing 3, 6, 12, 24, 36, 48, and 60 months of treatment with BRV will be provided. This analysis will be based on the duration of exposure to BRV as defined in Section 3.2.7. Subjects who have permanently discontinued will be analyzed as events on the last day of treatment with study drug; subjects who complete the study will be censored on the last day of treatment with study drug.

The date of first subject in (date of earliest Visit 1), date of last subject out (date of last scheduled or unscheduled visit), number of enrolled subjects, and the number of subjects in each analysis set or seizure type will be summarized overall and by investigator site. Subjects who transferred sites will be summarized according to their original site.

5.2 Protocol Deviations

The number and percentage of subjects with at least 1 important protocol deviation will be summarized overall and by category of protocol deviation for the Safety Analysis Set.

6 DEMOGRAPHICS AND OTHER BASELINE CHARACTERISTICS

6.1 Demographics

Demographics summaries will be based on demographic data from follow-up studies for subjects who enrolled in a follow-up study that collected demographic data. Otherwise, demographics summaries will be based on demographic data collected in the previous double-blind study.

Age, age category (<17, 17 to <65, and ≥65 years), gender, racial group and overall racial group (see below), body weight (kg), height (cm), body mass index (BMI) (kg/m²), and BMI category (<18.5, 18.5 to <25, 25 to <30, 30 to <40, ≥40) will be summarized for the Safety Analysis Set. Demographic data will be summarized overall and by subgroup for seizure type and geographic region.

Racial group was not collected in a consistent manner across studies. For this reason, racial group will be collapsed as follows for statistical summaries:

Category	CRF Racial Group
American Indian/Alaskan Native	American Indian/Alaskan Native
Asian	Asian, Asian/Pacific Islander, Indian/Pakistani
Black	Black, African-American
Native Hawaiian or Other Pacific Islander	Native Hawaiian or Other Pacific Islander
White	White, Caucasian, Hispanic
Other/Mixed	Other, Other/Mixed, Mixed Race

moreover, the overall racial group will be collapsed as follows for statistical summaries:

Category	Racial Group from Previous Study
White	White, Caucasian, Hispanic

Black	Black, African-American
Asian	Asian, Native Hawaiian or Other Pacific Islander, Asian/Pacific Islander, Indian/Pakistani
Other	American Indian/Alaskan Native, Other, Other/Mixed

All subjects should be classified into one of the above categories.

Racial group, ethnicity (Hispanic or Latino, Not Hispanic or Latino), and racial subgroup (Indian/Pakistani, Japanese, Other) were not collected in a consistent manner across all studies; these variables will be provided in subject data listings if available in the clinical data from the previous study but will not be summarized.

